# 6.1.2.4 INFECTION PROPHYLAXIS AND THERAPY

Antifungal prophylaxis will be administered according to institutional guidelines. Antifungal prophylaxis should begin no later than day 5 and continue until the absolute neutrophil count (ANC) is >500/microliter for 3 consecutive days (or for 2 consecutive measurements over a 3 day period) and the patient is free of evidence of infection. Antifungal prophylaxis can be substituted for patient intolerance or at the discretion of the treating physician.

Viral prophylaxis will be administered according to institutional guidelines. Standard options include, but are not limited to, valacyclovir (500mg po tid) or acyclovir (62.5 mg/m2 IV every 4 hours, if not tolerating oral medication) starting at day 1 of chemotherapy.

Antibiotic prophylaxis will follow institutional guidelines for induction therapy for acute myeloid leukemia/MDS.

Antibiotics will be administered at least until the ANC is >500/microliter following induction.

Empiric or directed treatment of suspected or active infections will supersede prophylactic therapy.

[figure not shown]
### 6.1.2.5 SUPPORTIVE CARE

Supportive care including fluids, anti-emetics, and tumor lysis management will be indicated according to institutional guidelines and the judgment of the treating physician.

#### 6.1.2.6 TRANSFUSION SUPPORT

Platelet and packed red cell transfusions will be given per current institutional recommendations.

### 6.1.2.7 TREATMENT SCHEME

The figure shows the protocol schema as planned for patients undergoing standard 7+3 induction chemotherapy.

The induction regimen may vary per judgment of the patient's provider.

### 6.1.3 DURATION OF THERAPY

Subjects are eligible for only one lymphocyte infusion. For the dose-escalation portion, a minimum of 2 subjects and a maximum of 18 subjects will be enrolled. There will be 3 dose levels in the dose-escalation portion. MTD is defined as the highest dose level with the probability of DLT less than 33% (DLT events are defined in Section 6). The DLT observation window is defined in section 9.4.2. If none of 3 patients experiences a DLT, we will escalate to the next dose level. If one of the 3 patients experiences a DLT, we will enroll 3 additional patients and treat at the same dose level. In this case, if none of these additional 3 patients experiences a DLT, we will escalate to the dosage to next level. If 2 or more patients among 6 enrolled patients experience a DLT, or 2 or more patients in the

3 patient cohort experience DLT, the dosage level exceeds the MTD and the previous dose level will be declared as the MTD. If the first dose level exceeds the MTD, the study will be suspended. If no subjects experience a DLT at any dose level, the MTD will be level 3 (5 x  $10^7$  CD4+ T cells/kg).

The RP2D is defined as the dose level selected to be evaluated in the expansion cohort or future phase II studies and will be equivalent to the MTD determined in the phase 1b portion of the study. Once we determine the RP2D level, we will enroll 10 additional eligible patients and treat with the RP2D level. The goal for this expansion cohort is to evaluate the safety and tolerability for patients who will be treated with NE-DLI in the RP2D dose level, and to evaluate the preliminary efficacy estimate for the ORR. Including the dose-escalation portion in which 3 or 6 enrolled patients will have been treated at the RP2D level, a total of at least 13 patients will be treated at the RP2D level. Based on previous data, (18) the complete response rate using microtransplantation was in the range of 36%-52% for MDS or AML from antecedent MDS patients. Hence, for the phase 2 portion, an ORR of 45% is considered clinically meaningful. With a sample size of 13 patients, if our ORR is 45%, the 95% CI (exact binomial) will be (18%-74%); if the ORR is 50%, the 95% CI will be (22%-78%).

The maximum total number of patients enrolled in this study will be 28 (6 per dose level plus 10 in the expansion cohort). We expect that the accrual rate will be one patient per every 5-6 weeks. With the DLI observation window, the dose-escalation portion may take up to a maximum of 2.5 - 3 years to complete and an additional 1.5 years for the expansion cohort.

# 6.1.3.1 DURATION OF FOLLOW-UP

Patients will be followed for a minimum of 56 days after DLI (day 0 is defined as the date of DLI infusion) and then until initiation of conditioning therapy for allogeneic stem cell transplantation, death, disease progression/relapse, or 1 year following the date of infusion, whichever occurs first. Patients removed from study for unacceptable adverse events or who develop treatment-related adverse events will be followed until resolution or stabilization of the adverse event. Patients who proceed to allogeneic stem cell transplantation will be removed from the study.

Post-infusion monitoring: Whole marrow and/or peripheral blood T-cell (CD3) donor cell chimerism will be measured after neutrophil recovery (ANC  $\geq$  500/ $\mu$ l) and no later than the day 42 sample collections to rule out engraftment. If donor chimerism is detected, this test will be repeated on day 56 and then monthly until graft rejection is confirmed. Non-hematologic toxicity will be assessed weekly while subjects are hospitalized, and weekly until day 42.

Disease assessment: Disease restaging requirements are designated in section 1.3.

In addition to disease assessments specified above, results of additional disease assessments performed as standard of care will be collected for study purposes until death or disease progression, whichever occurs first.

Off study criterion is the first event of the following:

- Death
- Disease progression
- One year after infusion (final study visit)

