#### 7.2 PARTICIPANT DISCONTINUATION/WITHDRAWAL FROM THE STUDY

Patients may elect to withdraw from the study at any point without any further justification.

Additionally, patients may be removed from the study at the discretion of their medical providers on the basis of the following criteria:

- Adverse events or any concern that continuing in the study would be harmful
- Need for treatment not allowed in the study, including disease relapse while on study
- Failure by a patient to comply with study protocol
- Onset of pregnancy after enrolling in the study
- Cancellation of the study

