#### 8.4.2 DEFINITION OF SAE

An SAE is any sign, symptom or medical condition that emerges during treatment or during a post-treatment follow-up period that (1) was not present at the start of treatment and is not a chronic condition that was part of the patient's medical history, OR (2) was present at the start of treatment or as part of the patient's medical history but worsened in severity and/or frequency during therapy, AND that meets any of the following regulatory criteria:

- is fatal (i.e., results in death from any cause at any time) or life-threatening (i.e., the patient was in the view of the investigator, at immediate risk of death from the reaction as it occurred)
- required or prolonged hospitalization (see exclusions below)
- results in persistent or significant disability/incapacity
- constitutes a congenital anomaly or a birth defect
- is medically significant, may jeopardize the subject and may require medical or surgical intervention to prevent one of the outcomes listed above.

Events not considered to be SAEs are hospitalizations for the:

- Routine treatment or monitoring of the studied indication, not associated with any deterioration in condition
- Treatment, which was elective or pre-planned, for a preexisting condition that did not worsen

Serious adverse events occurring in a patient from the first day of treatment and until 4 weeks after the last dose of treatment must be reported. The period after discontinuing study drug may be extended if there is a strong suspicion that the drug has not yet been eliminated.

All serious adverse events must be followed to resolution (≤ 1 or baseline) or until considered stable or irreversible.

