# 8.4.4 TIME PERIOD AND FREQUENCY FOR EVENT ASSESSMENT AND FOLLOW-UP

The occurrence of an AE or SAE may come to the attention of study personnel during study visits and interviews of a study participant presenting for medical care, or upon review by a study monitor.

AEs can be spontaneously reported or elicited during open-ended questioning, examination, or evaluation of a patient.

Grade 3-5 AEs, including local and systemic reactions not meeting the criteria for SAEs, will be captured on the appropriate CRF. Information to be collected will include event description, time of onset, clinician's assessment of severity, relationship to study product (assessed only by those with the training and authority to make a diagnosis), and time of resolution/stabilization of the event. All AEs occurring while on study must be documented appropriately regardless of relationship. All AEs will be followed to adequate resolution.

Any medical condition that is present at the time that the participant is screened will be considered as baseline and not reported as an AE. However, if the study participant's condition deteriorates at any time during the study, it will be recorded as an AE.

Changes in the severity of an AE will be documented to allow an assessment of the duration of the event at each level of severity to be performed. AEs characterized as intermittent require documentation of onset and duration of each episode.

All events beginning with start of study intervention until the first event of either starting allogeneic transplant conditioning, confirmed disease relapse, death, or 1 year from the of the trial cell infusion will be reported. At each study visit, the investigator will inquire about the occurrence of AE/SAEs since the last visit. Events will be followed for outcome information until resolution or stabilization.

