#### 8.4.5 AE REPORTING

The PI and/or the research nurse will monitor each patient closely for the development of adverse events and toxicities and record all such events. AEs will be recorded and reported in our annual report. As some toxicities are expected from the chemotherapy, we will compare incidence of toxicities to historical experience when using chemotherapy without the investigational DLI product. The FDA require the timely reporting of adverse events (including toxic deaths).

Each individual sign or symptom must be documented separately. Grade 3-5 adverse events (both expected and unexpected) will be captured on the appropriate study-specific CRFs.

An investigator must verify the attribution of all adverse events. Evaluation of laboratory toxicities may be documented on CRF provided the investigator signs it. However, if an action was conducted due to this abnormality (e.g., red blood cell transfusion due to low hemoglobin) this would be recorded on the AE form also.

AE reporting will begin at the time of cell infusion and continue through 1 year from day 0 or until loss to followup, death, disease progression, or proceeding to allogeneic BMT, whichever comes first. Subjects who proceed to allogeneic BMT will come off of the trial and will no longer be followed for AEs.

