# 8.4.6 SAE REPORTING

The study clinician will immediately report to the FDA any SAEs, whether or not considered study intervention related, including those listed in the protocol or investigator brochure and must include an assessment of whether there is a reasonable possibility that the study intervention caused the event. Study endpoints that are SAEs (e.g., all-cause mortality) must be reported in accordance with the protocol unless there is evidence suggesting a causal relationship between the study intervention and the event (e.g., death from anaphylaxis). In that case, the investigator must immediately report the event to the sponsor.

All SAEs will be followed until satisfactory resolution or until the site investigator deems the event to be chronic or the participant is stable. Other supporting documentation of the event may be requested by the DCC/study sponsor and should be provided as soon as possible.

It is the responsibility of the PI and the research team to ensure that SAEs are reported according to the Code of Federal Regulations, Good Clinical Practices, the protocol guidelines, the sponsor's guidelines, and IRB policy.

All adverse experience reports must include the patient number, age, sex, weight, severity of reaction (mild, moderate, severe), relationship to study drug (probably related, unknown relationship, definitely not related), date and time of administration of test medications, all concomitant medications, and medical treatment provided. The PI is responsible for evaluating all AEs to determine whether criteria for "serious" as defined above are present. Adverse drug reactions that are serious, unlisted/unexpected, and at least possibly associated to the drug, and that have not previously been reported in the IB, or reference safety information document should be reported promptly to the FDA in writing by each investigator/physician engaged in clinical research. A clear description of

the suspected reaction should be provided along with an assessment as to whether the event is drug or disease related.

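### Overall survival is censored at an undefined last follow-up date, and no vital-status collection is planned after progression or transplant

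*Combined protocol and SAP*

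**What the plan says.** **Endpoint and analysis.** The synopsis, section 3 and section 9.1 list OS as a secondary endpoint. Sections 9.4.1.1 and 9.4.9 measure it from treatment to death, censor it at the last follow-up date, and estimate it by Kaplan-Meier in the patients treated at the RP2D plus the expansion cohort. Neither section defines that date. Appendix B gives the OS event as death from any cause.

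**End of follow-up.** Section 6.1.3.1 sets a minimum of 56 days after the infusion, and then follow-up continues "until initiation of conditioning therapy for allogeneic stem cell transplantation, death, disease progression/relapse, or 1 year following the date of infusion, whichever occurs first". The same section adds: "Patients who proceed to allogeneic stem cell transplantation will be removed from the study". It closes with a list introduced by "Off study criterion is the first event of the following", which names death, disease progression and one year, but not transplant. Section 7.2 is softer: "patients may be removed from the study at the discretion of their medical providers", with relapse among the reasons.

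**Event reporting.**
- Section 8.4.2 counts death at any time as serious, but serious events "until 4 weeks after the last dose of treatment must be reported".
- Section 8.4.3.3 makes any death in the first 56 days after the infusion a serious adverse event.
- Section 8.4.4 reports events "until the first event of either starting allogeneic transplant conditioning, confirmed disease relapse, death, or 1 year" after the infusion.
- Section 8.4.5 reports through 1 year or until loss to follow-up, "death, disease progression, or proceeding to allogeneic BMT, whichever comes first".
- Section 8.4.6 says: "Study endpoints that are SAEs (e.g., all-cause mortality) must be reported in accordance with the protocol", with an exception where a causal link is suspected.
- Sections 6.1.3.1, 8.4.4 and 8.4.6 follow open adverse events to resolution or stabilization.

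**The concern.** Kaplan-Meier assumes that a patient censored at a given time has the same later risk of death as those still followed. If follow-up ends because the disease has progressed, the patient leaves when the risk of death rises. If it ends because the patient goes to transplant, the patient leaves because things went well, and then takes on a different risk. Neither exit is independent of survival.

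Section 2.1 presents the treatment as a bridge to transplant. The patients who reach that goal are therefore among those whose later survival would go unrecorded. Deaths that are not collected prospectively may not be recoverable at analysis, so this is a data-collection problem as well as one of wording.

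**Working it through.** **Step 1: put the passages together.** For a patient who progresses or starts conditioning, follow-up under 6.1.3.1 ends that day, or on day 56 if later. If that is the last follow-up date of 9.4.1.1, the patient is censored for OS then. Censoring at 1 year is administrative and not a problem.

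**Step 2: look for a passage that collects later deaths.**

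| Section | What it covers | Vital status after exit? |
|---|---|---|
| 1.3 and 8.1, schedule | 6-month and 1-year visits | No survival contact for patients off study |
| 7.3 | Patients who miss scheduled visits | Not those taken off study |
| 8.4.2 | Serious events to 4 weeks after last dose | No |
| 8.4.3.3 | Any death to day 56 | To day 56 only |
| 8.4.3.3.1 | GvHD until donor T-cell chimerism is below 5% or 1 year | Incidental only |
| 8.4.4, 8.4.5 | Stop at relapse or progression, and at transplant | No |
| 6.1.3.1, 8.4.4, 8.4.6 | Open events to resolution or stabilization | Only deaths linked to an open event |

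Some later deaths could be recorded, but no passage is a survival follow-up plan.

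**Step 3: illustrate the size.** The plan states no OS figure to reproduce.

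Inputs from the documents:
- Median OS of 6.5 months (sAML, 2.2.3.2) or 9 months (upper end of the figure for MDS after HMA failure, 2.2.3.1).
- 6% transplanted (elderly AML, 2.2.3.2).
- Median of 19.5 months after transplant, given as an upper figure (2.2.3.1).

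Assumed, because the documents are silent:
- Progression is 50%, 70% or 90% of non-transplant first events.
- Median survival after progression is 2, 3 or 5 months.
- Hazards are constant.

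The first event has total hazard h, with shares d (death), p (progression) and x (transplant). Later death hazards are m_p = ln2/(median after progression) and m_x = ln2/19.5. Then

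S(t) = e^(−ht) + Σ over k = p, x of [share_k · h · (e^(−ht) − e^(−m_k t)) / (m_k − h)].

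With every death counted to day 56 (1.84 months) and censoring at exit afterwards,

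KM(12) = S(1.84) · e^(−h·d·10.16).

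Middle case (6.5-month median, 6% transplanted, 70% progression, 3 months after progression):
- x = 0.06; p = 0.94 × 0.7 = 0.658; d = 0.94 × 0.3 = 0.282.
- Solving S(6.5) = 0.5 gives h = 0.217 per month.
- True S(12) = 0.074 + 0.117 + 0.042 = 0.232.
- S(1.84) = 0.864, so KM(12) = 0.864 × e^(−0.622) = 0.464.
- Deaths seen: (1 − 0.864) + 0.282 × (0.671 − 0.074) = 0.304, out of 1 − 0.232 = 0.768, which is 40%.
- For the minimum of 13 RP2D patients: 13 × 0.768 = 10.0 deaths, of which 13 × 0.304 = 4.0 are seen.

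Ranges over the nine splits. The transplant share is raised with h held at its 6% value:

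| Median OS, transplanted | True 1-year OS | As planned | Gap (points) |
|---|---|---|---|
| 6.5 mo, 6% | 21–27% | 30–74% | 3.0 to 52.5 |
| 6.5 mo, 20% | 29–34% | 36–77% | 1.5 to 47.5 |
| 6.5 mo, 40% | 40–45% | 46–82% | 1.4 to 40.6 |
| 9 mo, 6% | 36–38% | 47–83% | 8.2 to 46.6 |
| 9 mo, 20% | 42–45% | 52–86% | 7.3 to 42.0 |
| 9 mo, 40% | 50–55% | 61–89% | 7.3 to 35.5 |

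All 54 cases are upward. If the 20% or 40% share is instead reached by adding transplant hazard to fixed progression and death hazards, 3 of those 36 cases turn downward, by 1 to 9 points. The model gives no credit for deaths picked up through open adverse events after day 56.

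**The case against.** The strongest reply is that no sentence censors OS at progression or transplant. The last follow-up date could mean the date last known alive, and Appendix B already counts death from any cause. Section 7.2 makes removal at relapse discretionary, and the schedule note about omitting tests in relapsed patients suggests that some stay on study. This stands as far as it goes: the censoring is an inference from two sections. It does not supply a plan, however. If the date means last known alive, nothing says how that is learned after exit. If removal is discretionary, the censoring point varies from patient to patient.

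A reader might also infer that deaths after exit are never recorded. That is too strong, because the 56-day rule and the follow-up of open events would catch some.

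A reader might take 23% against 46% as the expected bias. The documents do not support that. They give neither the progression share nor survival after progression, and the inputs they do give come from different populations.

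Finally, OS here has no hypothesis or decision rule, 13 patients give wide limits in any case (exact 95% interval about 5–54% for 3/13 and 19–75% for 6/13), and one site may recover some death dates from records. All true, and this limits the consequence. But the interval around a biased estimate does not show the bias, and recovery from records is possible rather than planned.

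**Conclusion.** The point holds as a gap between the follow-up plan and the OS analysis. Followed as written, 6.1.3.1 with 9.4.1.1 and 9.4.9 gives informative censoring at progression or transplant, and no passage plans vital-status collection afterwards. The curve would then not reliably estimate death from any cause.

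Confidence is high that the plan is missing, and lower on how staff would read the last follow-up date in practice. The size is illustration only: 1.4 to 52.5 points at 1 year under the assumed splits, upward in most scenarios, with a few downward under the other transplant assumption. A claim that OS is certain to be overstated, or by a particular amount, goes beyond the documents.

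This should be fixed because OS is a named secondary endpoint. It does not touch the MTD, dose or stopping rules.

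**What to change.** **Section 6.1.3.1.** Keep the stop of study procedures as it is. Add that vital status and date of death are recorded by chart review or telephone to 1 year after infusion for every treated patient, regardless of progression, transplant or off-study status, subject to consent. Reconcile the off-study list (which omits transplant and has no 56-day exception), the sentence removing transplanted patients, and section 7.2.

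**Sections 9.4.1.1 and 9.4.9.** Define OS as time from treatment to death from any cause, censored only at the date last known alive or at 1 year. Label any analysis censored at transplant as a sensitivity analysis.

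**Cost.** Protocol wording, plus up to two brief vital-status checks per patient at the existing 6-month and 1-year time points, in at most 28 patients at one site. No extra visits or procedures are needed. The consent pages were not in the text reviewed, so the sponsor should check whether consent already allows this contact.

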### 6.1.4 DEFINITION OF DOSE-LIMITING TOXICITY

Number of Patients with DLT at a Given Dose Level	Escalation Decision Rule	
0 out of 3	Enter 3 patients at the next dose level.	
≥ 2	Dose escalation will be stopped. This dose level will be declared the maximally administered dose <highest administered="" dose="">. Three (3 additional patients will be entered at the next lowest dose level if or 3 patients were treated previously at that dose.</highest>	
1 out of 3	
 
Enter at least 3 more patients at this dose level.
 
If 0 of these 3 patients experience DLT, proceed to the next dose level.
 
If 1 or more of this group experience DLT, then dose escalation is stopped, and this dose is declared the maximally administered dose. Three (3) additional patients will be entered at the next lowest dose level if only 3 patients were treated previously at that dose.
 
	
≤ 1 out of 6 at highest dose level below the maximally administered dose	This is generally the recommended phase II dose. At least 6 patients must be entered at the recommended phase II dose.	

